#### Clinic Follow Up Appointments

- Subjects will follow up in clinic between 1-2 weeks postoperatively from their discharge date
- Vitals and physical exam will be performed, and all subjects will be monitored for adverse events
- Subjects will be closely followed every 1-3 weeks for the first 2 months after surgery
- At 12 days postoperatively all subjects will be called or evaluated in clinic for the final screening for adverse events or pulmonary complications

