## **Outcome Measures**

- Primary
  - **Incidence of post-operative pulmonary complication within 14 days after surgery**
    - Postoperative pulmonary complication will be defined as
      - Atelectasis or infiltrate diagnosed by radiologist on any postoperative chest radiograph within first 14 days or discharge (whichever occurs first)
      - Pneumonia
        - *Diagnosis is suggested by a history of cough, dyspnea, pleuritic pain, or acute functional or cognitive decline, with abnormal vital signs (e.g., fever, tachycardia) and lung examination findings. Diagnosis should be confirmed by chest radiography or ultrasonography.* [15]
    - Chronic pulmonary obstructive disease exacerbation
      - *An event in the natural course of the disease characterized by a change in the patient's baseline dyspnea, cough, and/or sputum and beyond normal day-to-day variations, that is acute in onset and may warrant a change in regular medication in a patient with underlying COPD* [16]
    - Adult respiratory distress syndrome (Berlin definition)
    - Need for reintubation/mechanical ventilation
    - Need for non-invasive mechanical ventilation
  - Secondary
    - **Time to tracheostomy decannulation** (half days)

NCT05362526

IRB202102700

9/22/22

- **Hospital length of stay after surgery** (half days)
- **Need for antibiotics for pulmonary complication** (escalation to broad spectrum, addition of a second antibiotic, antibiotics past post-operative day 7)
- **Need for pulmonary physiotherapy** (acapella, flutter, etc.)
- **Discharge destination:** Home vs nursing facility vs rehabilitation

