### **Data Collection**

- Data will be recorded in the subject's medical record list and in their medication administration record. These entries are time stamped at administration. Research data will be collected in REDcap database.

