## **Statistical Analysis**

### Sample Size Rationale

A sample size of 164 patients, 82 in each arm, is sufficient to detect a clinically important difference of 20% in the proportion of postoperative pulmonary complications between arms using a two-tailed z-test of proportions with 90% power and a 5% level of significance. This 20% difference represents 10% of postoperative pulmonary complications using HFOT and 30% of postoperative pulmonary complications in the control arm. Assuming a 10% rate of withdrawal, we will need to recruit 91 patients per arm to be adequately powered to detect the difference.

An interim analysis of the proportion of postoperative pulmonary complications is planned after 100 subjects (50:50) are enrolled to assess whether there will be overwhelming evidence of a benefit from HFOT, as compared with conventional oxygen therapy, or of harm in any study group. As a consequence, the p-value for the primary comparison between the two arms will be adjusted to conserve an overall significance level of 0.05[17]. Descriptive summaries will be frequencies and percentages for categorical variables and means, standard deviations, medians, and quartiles for continuous variables. The primary analysis will compare the difference in the proportion of postoperative pulmonary complications

between the intervention group and the control group. This difference is assessed using univariate analyses and ANCOVA (Analysis of Covariance) models. Demographic and baseline characteristics between groups are assessed using the non-parametric Wilcoxon Rank-Sum test for continuous data, and Pearson Chi-squared test or Fisher's Exact test (when expected frequencies are small) for categorical data. The secondary outcomes will be analyses using the same statistical methods, based upon the data distributions. Data analyses will be performed by a statistician with the Center for Data Solutions.

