### **Data Safety Monitoring Board**

- No experimental interventions are taking place, as HFOT tracheostomy delivery and conventional oxygen therapy are both well established and widely used modalities.
- The PI will monitor for any adverse events. If any adverse events are identified, they will be reported to the IRB in the required time frames.

**Anticipated study duration:** 14-24 months

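### The primary endpoint runs to day 14, but the last assigned screening for pulmonary complications is on day 12, so days 13–14 have no assigned endpoint ascertainment.

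*Combined protocol and SAP*

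**What the plan says.** The Outcome Measures section defines the primary outcome as "Incidence of post-operative pulmonary complication within 14 days after surgery". Its components are atelectasis or infiltrate on a chest film, pneumonia, COPD exacerbation, ARDS, reintubation or mechanical ventilation, and non-invasive ventilation. Only the film component carries a discharge cut-off: "Atelectasis or infiltrate diagnosed by radiologist on any postoperative chest radiograph within first 14 days or discharge (whichever occurs first". The others have none.

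The Clinic Follow Up Appointments section sets the last contact that names the endpoint: "At 12 days postoperatively all subjects will be called or evaluated in clinic for the final screening for adverse events or pulmonary complications". It also plans routine care. On the first visit it says "Subjects will follow up in clinic between 1-2 weeks postoperatively from their discharge date", and it then plans visits at intervals of one to three weeks over the two months after surgery. The stated content is "Vitals and physical exam will be performed, and all subjects will be monitored for adverse events".

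Two other sections bear on capture. Data Collection says that data go into the subject's "medical record list and in their medication administration record", with research data held in REDCap. The Data Safety Monitoring Board section says "The PI will monitor for any adverse events". Neither gives a date through which the primary endpoint is to be looked for.

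**The concern.** The screening that the plan itself calls final comes two days before the endpoint window closes. A patient at home who has a qualifying event on day 13 or 14 is counted only if someone happens to learn of it.

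Reintubation, ventilation or ARDS would normally leave a record somewhere. A COPD exacerbation may not, because the definition rests on a change in symptoms that need not lead to a change in medication. An event treated at another hospital may also be absent from the record the study team sees.

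Two things are at stake. The trial would report a 14-day incidence that was not systematically collected for 14 days. And events lost in the same proportion from both arms shrink the observed difference and cost some power.

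**Working it through.** **1. The dates.** Window end (Outcome Measures) minus last assigned screening (Clinic Follow Up Appointments): 14 − 12 = 2 days, namely days 13 and 14.

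**2. Does the first routine visit close the gap?** Counting 7 to 14 days from discharge, and starting at day 4 because a shorter stay is listed as a possible reason for withdrawal:

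| Discharge day | First visit, postoperative day |
|---|---|
| 4 | 11–18 |
| 5 | 12–19 |
| 6 | 13–20 |
| 7 | 14–21 |

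For discharge on days 4–6 the first visit can fall before day 14. For discharge on day 7 or later it falls on or after day 14 and could elicit late events in retrospect. So could the later visits over the two months. None of them is assigned that task.

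**3. Which events are exposed?** Film-diagnosed atelectasis or infiltrate closes at discharge, so a discharged patient cannot lose such an event on days 13–14. Exposure is confined to the other components in patients already at home.

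**4. The plan's own figure.** Inputs from Sample Size Rationale: "10% of postoperative pulmonary complications using HFOT and 30% of postoperative pulmonary complications in the control arm", two-sided 5% level, 90% power, 82 per arm. With the pooled z-test and p̄ = 0.20:

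- n = [1.96·√(2·0.20·0.80) + 1.2816·√(0.30·0.70 + 0.10·0.90)]² / 0.20² = (1.1087 + 0.7020)² / 0.04 = 81.96, so 82 per arm. The stated figure reproduces.
- Power = Φ{[√82·0.20 − 1.1087] / 0.5477} = Φ(1.28) = 90.0%.
- Expected events: 82 × (0.30 + 0.10) = 32.8.

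**5. Illustrative loss.** The documents give no event timing, so a constant hazard over 14 days is assumed, with everyone home by day 12 and nothing recovered from records or later visits. The proportion with an event by day 12 is 1 − (1 − p)^(12/14):

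- Control: 1 − 0.70^(12/14) = 26.3%, so 1 − 26.3/30 = 12.2% of events come later.
- HFOT: 1 − 0.90^(12/14) = 8.6%, so 13.6% of events come later (unrounded, 8.635%).

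If a share e of events belongs to the exposed components (assumed equal in both arms and with the same timing), the observed rates are 0.30·(1 − 0.122e) and 0.10·(1 − 0.136e):

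| e | Control v HFOT | Difference, points | Events missed of 32.8 | Power at 82 per arm |
|---|---|---|---|---|
| 0 | 30.0% v 10.0% | 20.0 | 0 | 90.0% |
| 25% | 29.1% v 9.7% | 19.4 | 1.0 | 89.0% |
| 50% | 28.2% v 9.3% | 18.9 | 2.1 | 87.9% |
| 100% | 26.3% v 8.6% | 17.7 | 4.1 | 85.4% |

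The last row treats film-diagnosed events as losable after discharge, which point 3 rules out, so it overstates the loss. Spreading all events evenly over 14 days instead (2/14 = 14.3% lost from each arm) gives 83.6%, with the same overstatement. All rows treat 30% and 10% as true 14-day rates and use a single-look test, without the interim adjustment.

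**The case against.** The strongest reply is that patients are not lost from view after day 12. Visits continue for two months, the investigator monitors adverse events, and data come from the medical record. Most exposed components are hard to miss: pneumonia should be confirmed by imaging, and ARDS, reintubation and non-invasive ventilation require acute care. The day-4 film, planned for every patient, may supply many of the events, and those are not at risk. All of this stands, and it is why the size is put as small. It does not supply a step that collects the endpoint through day 14.

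A reader might infer more than the documents support:

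- *That there is no contact after day 12.* The two-month visit schedule contradicts this. What is missing is assigned endpoint collection.
- *That the plan screens inpatients to day 14 but discharged patients only to day 12.* The day-12 screening applies to all subjects, and no section sets inpatient endpoint screening to day 14. Inpatients on days 13–14 are presumably observed in ordinary care, but that is an inference.
- *That the comparison is biased toward one arm.* The trial is non-blinded, so unscheduled capture could differ by arm, but nothing in the documents gives a direction or size.
- *That closing the film component at discharge is a further error.* It is an openly stated choice, and no error follows from it here.

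**Conclusion.** The mismatch is certain: both dates stand in the current text, and no other section reconciles them. The consequence is uncertain and probably small. If a quarter to a half of events are of the exposed kind, about one to two of 32.8 expected events would be missed and power would fall by about 1 to 2 points, to 89.0% or 87.9%. Those figures rest on the assumed exposed share, the constant hazard, universal discharge by day 12 and no recovery. Front-loaded events, later discharge or partial recovery from records would each make the loss smaller. The 85.4% figure should not be read as the expected power. The point should be fixed because it concerns how the primary endpoint is ascertained and costs almost nothing to repair; it does not rest on demonstrated harm.

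**What to change.** In Clinic Follow Up Appointments, move the existing final call or visit from day 12 to day 14 or shortly after, and have it ask about pulmonary events from surgery through day 14, including care received elsewhere. In Data Collection, state that the medical record is reviewed for the primary endpoint through day 14 in both arms. The follow-up section then agrees with Outcome Measures.

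No visit, film or patient is added, and the sample size stays at 82 per arm before withdrawal. The only downside is that the existing contact takes place at least two days later. Shortening the endpoint window to day 12 would also reconcile the sections, but it changes the primary outcome, whereas moving the contact leaves it intact.

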#### **Potential adverse events that could result in subject withdrawal from the trial:**

- Subjects unable to be extubated in the operating room after surgery
- Subjects who cannot tolerate COT or HFOT for the specified amount of time each day
- Subjects with surgical complications requiring significant alteration of the treatment plan
  - Subjects requiring a return to the operating room during their admission will be excluded, unless it is for a procedure not related to the original surgery

NCT05362526

IRB202102700

9/22/22

occurring after post op day 3, such as a gastrostomy tube or long-term IV access.

- Subjects who do not stay in the hospital for at least 4 days after surgery

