#### Randomization

- Randomization will be assigned by the study coordinator once the patient completes the consent process.
- Patients will be divided into three subgroups after enrollment: no free flap, free flap, and laryngo-pharyngectomy
- Randomization into COT vs HFOT will be performed based on a block randomization scheme, stratified by subgroup- no free flap, free flap, or laryngo-pharyngectomy.
- This system will be used to ensure well-balanced distribution into these three subgroups and in the two arms.
- The goal will be to always keep enrollment balanced accordingly to the usual volume of no free flap, free flap, or laryngo-pharyngectomy among the two treatment groups.
- The block randomization scheme will be generated by the analyst with the Center for Data Solutions at the UF College of Medicine Jacksonville, FL and it will be uploaded into REDCap before the data collection.

NCT05362526

IRB202102700

9/22/22

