### Operating Room

- In the operating room, patients will undergo their surgery per normal operating protocol. No patients will be treated differently because of the study.
- At the end of the procedure all patients requiring tracheostomy will have a size 8-0 cuffed Portex trach placed, the cuff will be deflated within 3 hours of leaving the operating room. Total laryngectomy patients will have a laryngectomy tube placed at end of procedure.
- The Anesthesia team will be instructed to treat the patients according to their normal standard of care for head and neck surgery
- All patients must be extubated prior to leaving the operating room, or else they will be dropped from the study
- Subjects will leave the operating room and be transported to the post anesthesia care unit for appropriate monitoring prior to being transferred to a progressive floor
- Starting at the PACU, tracheostomy patients will be started on COT or HFOT via tracheostomy adapter , until occlusive capping of the tracheostomy is tolerated. Once the trach is capped, patients can be placed on oxygen via nasal cannula if it is required to maintain O2 saturation levels as stated below.. Total laryngectomy patients will remain on COT or HFOT via trach mask adapter from the time they are in PACU until the time they can tolerate HME (heat moisture exchange) use or are discharged from the hospital, whichever comes first.

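### Patients can be removed after randomisation, and the plan names no analysis set and no outcome collection for them, so removals that depend on arm could bias the primary comparison; bias is possible, not shown.

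*Combined protocol and SAP*

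**What the plan says.** **Timing.** The Randomization section states: "Randomization will be assigned by the study coordinator once the patient completes the consent process". Consent is obtained before surgery. The Operating Room section has study oxygen begin later: "Starting at the PACU, tracheostomy patients will be started on COT or HFOT via tracheostomy adapter". Every removal rule below therefore acts on patients who already have an assigned arm.

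**Removals in firm wording.**
- Operating Room: "All patients must be extubated prior to leaving the operating room, or else they will be dropped from the study".
- Withdrawal section: "Subjects requiring a return to the operating room during their admission will be excluded, unless it is for a procedure not related". The exception covers unrelated procedures done after postoperative day 3. This is a sub-item under a heading that is itself conditional.

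**Removals in conditional wording**, listed under "Potential adverse events that could result in subject withdrawal from the trial":
- Device intolerance: "Subjects who cannot tolerate COT or HFOT for the specified amount of time each day"
- Complications: "Subjects with surgical complications requiring significant alteration of the treatment plan"
- Short stay: "Subjects who do not stay in the hospital for at least 4 days after surgery"

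**Analysis.** The Statistical Analysis section compares the proportions with pulmonary complications by univariate analyses and ANCOVA. It names no intention-to-treat, modified or per-protocol set and no method for missing outcomes. It raises 82 per arm to 91 for 10% withdrawal.

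**Follow-up.** Day of Surgery says that patients who drop out are treated with COT, and is silent on their data. Clinic Follow Up Appointments provides a final contact with all subjects at day 12, without saying whether withdrawn or excluded patients are included. Outcome Measures sets a 14-day primary window. Data Collection relies on time-stamped medical records. Study Design describes the trial as non-blinded.

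**The concern.** If the share removed differs by arm, and removed patients differ in risk from those who stay, the analysed groups are no longer the randomised groups. The difference in complications can then be biased in either direction. Intolerance is defined by the assigned device, so it can differ by arm. The 4-day rule selects on length of stay, which is itself a secondary outcome: if one arm shortens stay, its quickest recoveries may be the patients removed.

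The primary outcome includes reintubation and ventilation. A patient heading towards either may first stop tolerating the assigned oxygen. This is an inference, but it shows how removal and outcome could be linked. Because the trial is non-blinded and no analysis set is named, the choice of who counts also stays open until outcomes are known.

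**Working it through.** **1. The plan's own figure.** Inputs from Sample Size Rationale: 30% v 10%, two-sided 5%, 90% power. With mean proportion 0.20:

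n = [1.960·√(2·0.20·0.80) + 1.282·√(0.30·0.70 + 0.10·0.90)]² / 0.20² = 81.96, so 82 per arm, with power 90.0%. The stated figure reproduces. Then 82/0.9 = 91.1, which the plan gives as 91 (91 × 0.9 = 81.9). The sample size is not at fault.

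**2. Bias if removed patients leave the analysis.** The documents give only one overall 10% withdrawal figure, with no split by arm or risk. The removal shares e and the risk r among removed patients below are therefore assumptions. Assume also no true effect, risk p = 0.30 in both arms, 91 randomised per arm and one unadjusted 5% test.

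- Analysed rate per arm = (p − e·r)/(1 − e); analysed n = 91(1 − e).
- Rejection probability = Φ[(|d| − 1.96·s₀)/s₁] + Φ[(−|d| − 1.96·s₀)/s₁], where d is the difference in analysed rates, s₀ the pooled and s₁ the unpooled standard error.

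| Removed, HFOT v COT | r | Analysed rates, HFOT v COT | Type I error |
|---|---|---|---|
| 10% v 10% | 60% | 26.7% v 26.7% | 5.0% |
| 5% v 3% | 60% | 28.4% v 29.1% | 5.1% |
| 12% v 8% | 60% | 25.9% v 27.4% | 5.5% |
| 10% v 5% | 60% | 26.7% v 28.4% | 5.7% |
| 15% v 5% | 60% | 24.7% v 28.4% | 8.3% |
| 15% v 5% | 80% | 21.2% v 27.4% | 14.9% |
| 5% v 2% | 5% | 31.3% v 30.5% | 5.2% |

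Example, 15% v 5% at 60%: HFOT (0.30 − 0.09)/0.85 = 0.2471; COT (0.30 − 0.03)/0.95 = 0.2842; d = 0.0372, s₀ = 0.0692, s₁ = 0.0690; rejection probability 0.0828.

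In the three mild unequal cases the bias runs from 29.07 − 28.42 = 0.65 points to 28.42 − 26.67 = 1.75 points, against a design difference of 20. The 80% row is extreme: it deletes 0.15 × 0.80/0.30 = 40% of HFOT events. The last row, low-risk short stays, pushes the other way. Removal that is equal in share and risk leaves type I error at 5%.

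The interim look changes little. Under an assumed two-look O'Brien-Fleming rule at 50 of 91 per arm, simulated errors for 10/10, 12/8, 10/5 and 15/5 at 60% are 5.1%, 5.5%, 5.8% and 8.3%.

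**3. Power if all 91 per arm are analysed as randomised.** Hold COT at 30%. Let a share d of HFOT patients stop and carry risk r, the rest staying at 10%. The HFOT rate is 0.10(1 − d) + r·d.

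| d | r | HFOT rate | Power |
|---|---|---|---|
| 0 | – | 10% | 92.8% |
| 5% | 30% | 11% | 89.4% |
| 10% | 30% | 12% | 85.2% |
| 20% | 30% | 14% | 74.5% |
| 10% | 60% | 15% | 68.1% |

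The last row gives stopping patients the same 60% risk as most rows in step 2. For 90% power, d = 10% would need 106 per arm at r = 30% and 161 at r = 60%.

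**4. Short stays and the radiograph.** Oxygen Protocols schedules one film at the start of postoperative day 4. Outcome Measures counts radiographic atelectasis or infiltrate only to day 14 or discharge, whichever is first. A patient who leaves before day 4 may have no scheduled film, and the radiographic window has then closed. Nothing is formally missing, so a general missing-data rule would not catch such patients.

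**The case against.** **The firm rules are the weakest route to bias.** Failed extubation precedes study oxygen, and the documents give no reason why oxygen type would change reoperation. The rules most likely to depend on arm are only possible grounds for withdrawal. This stands: the documents do not show that those patients will be removed. Short stays may also be few, since Hospital Care and Figure 1 place the tracheostomy change on day 4. Yet Study Design admits diagnoses with a mean stay of three or more days, so they can occur.

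**The effect is small unless removal is strongly unequal.** This stands too. The 8.3% and 14.9% results need a threefold imbalance and at least double the risk among removed patients, and the documents support neither.

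**The 4-day rule may serve ascertainment.** The day-4 film makes that plausible, although the plan gives no such reason. Keeping short-stay patients and counting them as free of radiographic events could replace one arm-dependent bias with another. This stands and shapes the fix.

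**Outcomes may be collected anyway.** Records and the day-12 contact make much of this feasible. They do not commit the plan to it, and day 12 falls short of the 14-day window.

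**A stronger reading that fails.** A reader might infer that the trial is set up as a per-protocol analysis favouring HFOT. The rise from 82 to 91 is consistent with removed patients leaving the analysis but does not prove it. Neither the direction nor the size of any bias can be derived from the documents.

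**Conclusion.** The concern holds as a gap in the plan, not as a demonstrated bias. Stated rules remove randomised patients in a non-blinded trial, and neither the analysis set nor outcome collection after removal is defined. On assumed inputs the effect ranges from none (equal removal), through 5.1% to 5.7% type I error (mild imbalance), to 8.3% (15% v 5% removed at 60% risk). The actual figure cannot be known from the documents. The repair is inexpensive, so this is a worthwhile improvement rather than a fatal flaw. Confidence is medium, because it turns on how often the discretionary rules would be used.

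**What to change.** Settle these before outcomes are examined by arm, including at the 100-patient interim analysis:

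- **(a)** Make the primary analysis all randomised patients by assigned arm. Keep the current exclusions only for a per-protocol sensitivity analysis.
- **(b)** Leave clinical decisions to stop study oxygen unchanged, but separate them from leaving follow-up.
- **(c)** Collect the primary outcome for all randomised patients from existing records and contacts, where consent allows. Reconcile the day-12 final screening with the 14-day window.
- **(d)** Include short-stay patients in the length-of-stay analysis.
- **(e)** Do not silently count patients discharged without a postoperative film as free of radiographic events. Report film availability by arm, and add a sensitivity analysis that treats this component as missing.
- **(f)** Report removals by arm and reason.

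**Cost.** Protocol, SAP and consent wording, plus staff time to abstract the records of withdrawn patients. Some outcomes will still be missing where consent is withdrawn. The statistical downside is dilution, since patients who drop out are treated with COT. The sponsor should state the power range: 92.8% with no reversion, and 85.2% to 68.1% if 10% of HFOT patients stop, depending on their assumed risk. It need not enrol more patients.
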